13.5.4. Factor FVIII Product Usage

The annualized use of FVIII replacement products will be calculated for all patients and by dose

PROTOCOL

Title: Safety and Efficacy of Encapsulated Allogeneic FVIII Cell Therapy in Haemophilia A
Study No. SIG-001-121

cohort as the total number of uses of replacement products divided by the length of time on study product follow-up.

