5.1.2. Secondary Objectives

- To evaluate development of FVIII inhibitors after administration of SIG-001
- To characterize FVIII activity levels after administration of SIG-001
- To assess frequency of bleeding episodes following SIG-001 administration
- To assess effects of SIG-001 on usage of FVIII products

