5.2.2. Secondary Endpoints

- Factor VIII inhibitor titres (NBU)
- FVIII activity levels (one-stage and chromogenic assays)
- Bleeding rate (annualized; ABR)
- Total use of factor VIII therapies (annualized)

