Annualized bleeding rates and FVIII usage can also inform preliminary efficacy of SIG-001. Patients with haemophilia A with FVIII activity below 2% suffer frequent spontaneous joint bleeds, but annualized spontaneous joint bleeds are close to zero once sustained FVIII activity rises above 12% (den Uijl et al., 2011). A significant reduction in exogenous FVIII usage is

PROTOCOL

Title: Safety and Efficacy of Encapsulated Allogeneic FVIII Cell Therapy in Haemophilia A
Study No. SIG-001-121

expected in patients reaching those FVIII levels. Therefore, data on bleeding rates and FVIII usage after SIG-001 administration will be assessed prospectively throughout the study.

Finally, exploratory endpoints include (1) change in health and quality-of-life as measured by the EQ-5D-5L and Haem-A-QoL instruments, respectively as well as (2) change in the number of target joints and frequency of bleeding episodes in target joints, as well as change in joint health scores as measured by the HJHS instrument. Low health-related quality-of-life is a long-recognized issue in haemophilia patients due to the physical, social, and emotional costs of the disease and the burden of lifelong treatment. It will be important to determine whether SIG-001 is able to impact this important facet of haemophilia patient care. In addition, poorly sustained FVIII levels often result in breakthrough bleeds and subsequent chronic joint disease. The effects of SIG-001 on health, quality-of-life and target joints and joint health will all be monitored as exploratory endpoints.

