7.5.2. Criteria for Re-Starting Prophylactic Therapy

Patients may restart prophylaxis if their FVIII level is <2% normal activity in two separate occasions done at least one week apart after 8 weeks following SIG-001 placement. If a patient needs to restart prophylaxis prior to Week 8, the Investigator should contact the Medical Monitor for approval.

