7.5.3. Prohibited Medications and Therapies

Medications that increase the risk of bleeding or that are contraindicated for laparoscopic surgery per the site's standard of care will be prohibited. Examples may include use of aspirin or nonsteroidal anti-inflammatory drugs (NSAIDs) in the 5 days period prior to, and following SIG-001 administration.

Emicizumab is prohibited any time during the trial unless the patient has already met the criteria to restart prophylaxis.

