12.3.4. Mitigation of FVIII Inhibitor Development

New inhibitor formation in patients with haemophilia A and more than 150 exposure days to

PROTOCOL

Title: Safety and Efficacy of Encapsulated Allogeneic FVIII Cell Therapy in Haemophilia A
Study No. SIG-001-121

FVIII products is rare (Kempton, 2010). In addition, patients at higher risk of developing inhibitors such as those with current FVIII inhibitor titres > 0.6 NBU/mL or prior ITI are excluded from this study. Lastly, SIG-001 produces human FVIII with the same amino acid sequence of commercially available recombinant FVIII products that have a well-established safety profile (Mrooctocog alfa or BDDrFVIII; trade names ReFacto®, XYNTHA®), thus limiting the exposure of patients to neo-epitopes. As such, there is a small risk that SIG-001 administration may result in the development of FVIII inhibitors.

In the unlikely event of new development of FVIII inhibitors or persistently increased titres from baseline levels after SIG-001 administration, appropriate measures must be taken to ensure the safety and optimal care of the patient, including additional visit(s) for physical examination and frequent laboratory testing (including Bethesda assay for FVIII inhibitors). Clinical management will be instituted at the discretion of the Investigator and following established management guidelines (Carcao & Goudemand, 2018). Clinical management may range from monitoring alone to use of approved therapies to treat and prevent bleeds in patients with inhibitors, to institution of ITI. Should the Investigator consider that avoiding exposure to BDD-hFVIII produced by SIG-001 is necessary, removal of spheres may be considered (Section 12.3.3, Potential Removal of SIG-001 spheres).

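### Section 13.5.4 counts FVIII uses over all follow-up time, so a SIG-001 failure who moves to emicizumab appears as a low FVIII user and one who resumes FVIII as a high user

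*Protocol*

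**What the plan says.** The protocol lists annualised FVIII use as a secondary endpoint (5.2.2). Its objective is "To assess effects of SIG-001 on usage of FVIII products" (5.1.2), and 6.5.2 gives it an efficacy reading: "Annualized bleeding rates and FVIII usage can also inform preliminary efficacy of SIG-001".

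Section 13.5.4 fixes the calculation, for all patients and by dose "cohort as the total number of uses of replacement products divided by the length of time on study product follow-up". Nothing in 13.5 or 13.5.4 ends, splits or flags the time after a patient starts a different prophylaxis.

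On what a patient may take after failure, 7.5.2 states: "Patients may restart prophylaxis if their FVIII level is <2% normal activity in two separate occasions", at least a week apart and after Week 8. Section 7.5.3 adds: "Emicizumab is prohibited any time during the trial unless the patient has already met the criteria to restart prophylaxis". Section 3.2 describes emicizumab as a non-factor antibody. Section 6.6.1 keeps every dosed patient in follow-up for the whole study.

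**The concern.** Outside the inhibitor setting, the protocol opens emicizumab only to patients who meet the restart criteria, which in the ordinary case means FVIII below 2% twice, so that SIG-001 has failed. If such a patient resumes FVIII prophylaxis, the failure shows as high use. If he takes emicizumab, his FVIII use largely stops, the denominator runs on, and the failure shows as low use.

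The rate therefore measures how much FVIII was used whatever replaced it, while the objective asks what SIG-001 did to FVIII use. Switching is conditional on failure and moves the patient towards the favourable end of the scale, so the error is not random. Cohorts have 3 to 6 patients, and one such patient visibly shifts a cohort summary.

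**Working it through.** The protocol gives no figure for this endpoint to reproduce, so the 13.5.4 formula is applied to hypothetical patients in whom SIG-001 has failed.

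**Inputs from the protocol**
- Scheduled FVIII samples at Weeks 8, 10 and 12 (Table 2). Two low readings after Week 8 can be in hand by Week 12.
- FVIII prophylaxis k = 1 to 3 infusions per week (background text, 3.2).
- Key efficacy window of 52 weeks (13.5); full follow-up of 260 weeks (Table 2).
- FVIII continues until the Week 1 visit, possibly once or twice daily (9.2.4), and 13.5.4 does not exclude it.

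**Assumptions**
- Switch, or return to FVIII, at Week 12.
- Perioperative uses p = 7 to 14.
- On-demand uses before that point u = 0 to 1 per week, over 12 weeks.
- No FVIII use after a switch.

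**Share of time after the switch**
- Year 1: (52 − 12)/52 = 40/52 = 77%.
- Five years: (260 − 12)/260 = 248/260 = 95%.

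**Year 1 uses per patient**
- Resumes FVIII: a = p + 12u + 40k, from 7 + 0 + 40 = 47 to 14 + 12 + 120 = 146.
- Switches to emicizumab: b = p + 12u, from 7 to 14 + 12 = 26.
- Difference: 40k = 40 to 120 uses.

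With u = 0 the switched failure shows only his 7 to 14 perioperative uses. A patient with a working implant and no on-demand use would show the same.

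**Three failures, one of whom switches**

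Mean with all three on FVIII = a. Mean with one switched = (2a + b)/3. Relative fall = (a − b)/(3a) = 40k/[3(p + 12u + 40k)].

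| k | p | u | a | b | Mean, one switched | Fall |
|---|---|---|---|---|---|---|
| 1 | 14 | 1 | 66 | 26 | 52.7 | 40/198 = 20% |
| 1 | 7 | 0 | 47 | 7 | 33.7 | 40/141 = 28% |
| 3 | 14 | 1 | 146 | 26 | 106.0 | 120/438 = 27% |
| 3 | 7 | 0 | 127 | 7 | 87.0 | 120/381 = 31% |

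In absolute terms the mean of a cohort of three falls by 40k/3 = 13 to 40 uses in Year 1, whatever the other two patients do.

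**Second set of assumptions.** Take a Week 10 switch, 2 infusions per week, 14 perioperative uses and 0.75 on-demand uses per week over 9 weeks. Uses before the switch are 14 + 6.75 = 20.75. The patient who resumes FVIII has 20.75 + 2 × 42 = 104.75. One switcher moves the mean from 104.75 to (2 × 104.75 + 20.75)/3 = 76.75, a fall of 27%.

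**Does stopping the clock at the switch suffice?** Without perioperative uses, the pre-switch rate is 52u = 0 to 52 per year. With them it is (p + 12u) × 52/12 = 30 to 113 per year, with the Week 1 cover spread over only 12 weeks. Either way it describes the period when prophylaxis had been withdrawn and does not show that the patient went back to it.

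**The case against.** **The SAP may handle this.** Section 13.1 defers detailed methods to an SAP that is not available here. That would answer a silent protocol. This one states numerator and denominator, and following them exactly gives the distorted result.

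**The study is descriptive, and a failure would be visible elsewhere.** FVIII activity is summarised at each scheduled assessment, FVIII usage is listed by subject, and there are at most 18 patients. A careful reader could identify a switched patient. This limits the harm, but listings do not correct the cohort summary of a named secondary endpoint.

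**The illustration is strained.** Under 6.4, Patients 2 and 3 of Cohort 1 receive Dose 1 only if Patient 1 reaches 5 IU/dL at Week 8, so three early failures in that cohort are unlikely. Severe patients treated on demand are also eligible, and the infusion frequency is background text. These points stand: the percentages show direction and scale and are not a forecast.

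**Stronger readings that the documents do not support**
- A reader might infer that 13.5.4 credits SIG-001 with a reduction. It defines no change from baseline and attributes nothing; the efficacy reading comes from 5.1.2 and 6.5.2.
- A reader might extend the point to inhibitors, since 12.3.4 allows "use of approved therapies to treat and prevent bleeds in patients with inhibitors". That section does not say these therapies are non-FVIII, and it also lists immune tolerance induction, which would raise FVIII use if given with FVIII. The direction is uncertain.
- A reader might speak of years of dilution. The key analyses stop at Year 1, so about 40 weeks are affected there. The Years 2 to 5 analyses are promised in the synopsis but only optional in 13.5.
- Leaving out the perioperative doses would give 26% to 33%, but the formula includes them.

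**Conclusion.** The point holds for emicizumab. The 13.5.4 formula, the access rule in 7.5.3 and continued follow-up together make a failed patient who switches look like a low FVIII user, while the same failure on FVIII looks like a high user. The bias depends on outcome and favours the product; that direction follows from the text as long as a switched patient uses less FVIII than he would on FVIII prophylaxis.

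The size rests on the stated assumptions: about 20% to 31% off the mean Year 1 use of a cohort with one switcher among three failures. Whether any patient will switch is unknown; the protocol expressly permits it. The plan should be changed, but this does not undermine the trial's primary safety objective.

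**What to change.** Amend 13.5.4, with matching SAP text:

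1. By cohort, report the number of patients who returned to any prophylaxis, FVIII or non-FVIII, and the time to return. This is the essential part, because it shows a switch as a return to prophylaxis and not as FVIII saved.
2. Report annualised FVIII use split at the start of any non-FVIII prophylaxis, with the periods before and after shown separately, each over its own follow-up time.
3. Keep the whole-follow-up rate as a supplementary summary.

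The cost is wording and programming. Concomitant medications are collected throughout (7.5, 10.1.5), and FVIII treatment events are recorded in the diary (10.2.2). No clinical rule changes. The small downside is that the pre-switch rate of a switched patient covers a shorter period and is less precise.

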- b) Screening Visit 2 / Rescreening applies only to patients who have been determined to be eligible for the study but do not receive SIG-001 within the original screening window. Those subjects will be asked to return to the clinic for Screening Visit 2 / Rescreening to repeat select screening assessments. Patients must receive SIG-001 within 90 days of the original screening date. Subjects who fail screening assessments at Screening Visit 2 / Rescreening can rescreen once under a new subject ID.
- c) Patients should lie down for at least 5 minutes before the ECG assessment is performed. ECG assessments should be performed before vital sign assessments if possible. If blood samples need to be collected first, the ECG and vitals should be performed at least 10 minutes after blood sample collection.
- d) Vital signs include temperature, respiratory rate, seated blood pressure (BP), and pulse. Seated BP will be recorded after the patient has been sitting for at least 5 minutes. Three BP measurements will be recorded at screening, and the average will be calculated for eligibility assessment. After screening, a single BP measurement is sufficient.
- e) Diary training and completion of the weekly diary should be initiated only after the patient has been confirmed to be eligible for the study. Patients may be brought back for a separate visit to be trained on how to complete the weekly diary.
- f) FVIII usage history collected during screening will be based on medical records and patient recollection. During the hospital stay, FVIII usage will be recorded by hospital staff; otherwise, FVIII usage will be recorded by the patient in the electronic patient diary.
- g) If historical records are available, F8 genotyping does not need to be conducted at Screening.

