7.5.1. Permitted Medications and Therapies

Prior to the laparoscopic procedure, patients will receive a single dose of antibiotic (or a single dose of 2 different antibiotics), per the site's standard clinical practice.

Following the Week 1 visit, patients will be withdrawn from FVIII therapy per the Investigator's discretion. If FVIII therapy is continued after the Week 1 visit, the reason for continuation will be recorded.

On-demand FVIII use is allowed throughout the duration of the study for the treatment of bleeding episodes, perioperative management for surgery or other medical procedures, or preventative for vigorous physical activity. Each use of exogenous FVIII will be recorded and reported during the study.

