9.2.2. Pre-Procedure Activities

Prior to laparoscopic administration of SIG-001, patients will be dosed with a bolus of plasma-derived or rFVIII (depending on the type of product the patient was receiving and hospital requirements), followed by maintenance FVIII administration either as repeat bolus administrations or as a continuous infusion, per Investigator's and/or site's standard clinical practice. The laparoscopic procedure will proceed ONLY if:

- a) pre-surgical FVIII activity levels reach ≥ 60 IU/dL (60% of normal) obtained within 1 hour of FVIII infusion
OR
- b) pre-surgical aPTT is normal AND measured pre- and post- dosing FVIII levels (IU/dL) reach a difference of at least 60% during PK assessment. This FVIII level difference may have been determined during prior screening visits, per the Investigator's judgment and preference.

PROTOCOL

Title: Safety and Efficacy of Encapsulated Allogeneic FVIII Cell Therapy in Haemophilia A
Study No. SIG-001-121

Prior to the laparoscopic procedure, patients will receive a single dose of one antibiotic (or a single dose of 2 different antibiotics), as per the site's standard clinical practice.

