9.2.4. Post-Procedure Activities

Following SIG-001 administration, patients will continue to receive FVIII to maintain trough levels $\geq 60\%$ for the first 48 hours after surgery. Patients may be discharged from the hospital on Day 3 or later per the Investigator's discretion.

FVIII dosing will be continued at home until the 1-week visit, to maintain minimal haemostatic trough levels of $\geq 30\%$ of FVIII activity. This post-procedure FVIII treatment regimen may involve twice daily dosing for standard half-life products or once daily dosing for extended half-life products. Patients may be discharged with a PICC line as needed. Per the Investigator's discretion, patients may remain in the hospital for longer observation during FVIII administration.

Patients will be withdrawn from FVIII therapy after the Week 1 (Day 7) visit, per the Investigator's discretion. If patients are not withdrawn from FVIII therapy at Week 1, the reason for continuing FVIII will be recorded.

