10.2.2. Bleeding Events and FVIII Usage

The number of bleeding events and quantity of FVIII replacement product used will be collected. At screening, the number of bleeding events and usage of FVIII replacement product will be documented for the past 12 months based on medical history and patient recollection. Bleeding events will be recorded by the patient as part of the patient diary. For each bleeding episode, the following parameters will be recorded: location (joint, muscle, internal organ vs other), type of bleed (spontaneous, traumatic, procedure-related), severity, and action taken/treatment.

Annualized bleeding rate will also be categorized by bleed location (joint, muscle, internal organ, other) and type of bleed (spontaneous, traumatic, procedure-related). Recombinant FVIII replacement therapy during the follow-up period will be recorded by the patient as part of the treatment diary. The following parameters will be recorded for each treatment event: reason for replacement therapy, name of product used, and dose.

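### Section 13.5.4 measures annualised FVIII use by a count of uses alone and does not separate the home FVIII that covers the SIG-001 procedure

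*Protocol*

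**What the plan says.** The secondary endpoint in Protocol Section 5.2.2 is annualised total use of factor VIII therapies, with no unit. The only working definition is in Section 13.5.4, for all patients and by dose cohort: "the total number of uses of replacement products divided by the length of time on study product follow-up". It names no amount, no split by reason or product, and no excluded period.

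Section 10.2.2 says that the quantity of product is collected and that each treatment event carries "reason for replacement therapy, name of product used, and dose".

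On cover for the procedure, Section 9.2.4 states that "FVIII dosing will be continued at home until the 1-week visit", and that this regimen "may involve twice daily dosing for standard half-life products or once daily dosing for extended half-life products". Note f to Table 2 has hospital staff record usage during the stay; "otherwise, FVIII usage will be recorded by the patient in the electronic patient diary". So the home doses enter the same usage record as later doses.

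**The concern.** Two features of the formula weaken the endpoint.

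First, a count ignores amount. Two patients with the same number of infusions score the same whatever the dose, and a product given twice daily scores double one given once daily over the same days. The endpoint is meant to show how far SIG-001 reduces the need for exogenous FVIII, and amount is part of that.

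Second, home FVIII up to the Week 1 visit is given because of the surgery. It says nothing about whether SIG-001 works. If it is counted, a patient who needs no FVIII for bleeds or prophylaxis cannot score zero, and the size of the non-zero score depends on product half-life. With at most six patients per cohort, the mix of products can move a cohort summary.

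**Working it through.** The protocol gives no figure to reproduce, so the formula was applied as written.

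**Inputs**
- Frequency: 2 per day (standard half-life) or 1 per day (extended half-life), from Section 9.2.4, which says what the regimen may involve. Treated here as an assumption.
- Week 1 visit on Day 7 (Section 9.2.4); the Table 2 window of ±2 days gives Day 5 to Day 9.
- Start of follow-up: after Day 3. The synopsis names three periods (screening, SIG-001 administration, follow-up), and Table 2 places Day -1 to Day 3 under administration.
- Time point: Week 52, because Section 13.5 bases the key efficacy analyses on data to the end of Year 1.
- Scale: replacement 1 to 3 times per week (Section 3.2).

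**Procedure cover inside follow-up**
- Days 4 to 7 are 4 days: 2 × 4 = 8 uses, or 1 × 4 = 4 uses.
- Visit on Day 5: 2 days, so 4 or 2 uses. Visit on Day 9: 6 days, so 12 or 6 uses.

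**Annualised score with no later use**
- Time = (364 − 3)/365.25 = 0.988 years.
- Twice daily: 8/0.988 = 8.1 per year (4.0 to 12.1 over the visit window).
- Once daily: 4/0.988 = 4.0 per year (2.0 to 6.1 over the visit window).
- With procedure cover left out: 0 for both.

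**With k later uses (k assumed), Day 7 visit**

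| k | Twice daily: (8+k)/0.988 | Once daily: (4+k)/0.988 | Ratio | Cover left out: k/0.988 |
|---|---|---|---|---|
| 5 | 13.2 | 9.1 | 1.44 | 5.1 |
| 10 | 18.2 | 14.2 | 1.29 | 10.1 |
| 20 | 28.3 | 24.3 | 1.17 | 20.2 |

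The absolute offset is the same in every row. Only its relative weight falls as later use rises.

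**Scale**
- 1 × 52 = 52 to 3 × 52 = 156 uses per year.
- 4/156 = 2.6% and 8/52 = 15.4%, so about 3% to 15%.

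**Sensitivity to the start of follow-up**
- If follow-up began on Day 1: 7 days give 14 or 7 uses; 364/365.25 = 0.997 years; 14.0 or 7.0 per year.

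**Blindness to amount**
- Ten uses in a 70 kg patient at 20 or 50 IU/kg (illustrative values, not from the protocol): 10 × 20 × 70 = 14,000 IU and 10 × 50 × 70 = 35,000 IU. The count is 10 in both cases; the amount differs 2.5-fold.

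**The case against.** **Detail belongs in the SAP.** Section 13.1 leaves detailed descriptions to the SAP, which is not shown and may add IU/kg or a split by reason. That stands for detail the protocol leaves open. But Section 13.5.4 states a formula, and that formula gives about 4 or 8 where the informative value is 0. The SAP would have to supplement or depart from it.

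**A count is legitimate.** This stands. The endpoint names no unit, and Section 6.5.2 gives sparing patients frequent infusions as a goal. A reader might infer that the count contradicts the endpoint; it does not. It is incomplete on its own.

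**Listings help.** The synopsis promises descriptive summaries and subject listings of FVIII usage. With at most 18 patients, listings carrying dose, product and reason would let a reader see procedure cover case by case. Their content is not specified, so this softens the point without removing it.

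**All procedure FVIII is counted.** A reader might infer that the formula takes in everything given around surgery, including the pre-operative bolus and the maintenance FVIII that Section 9.2.2 describes as "followed by maintenance FVIII administration either as repeat bolus administrations or as a continuous infusion". On that reading the offset would be 7 to 14 uses per year, and a continuous infusion would have no natural count. Section 6.2, which speaks of 5 years of follow-up after administration, leaves room for this. The synopsis and Table 2 support it less, because they put Day -1 to Day 3 in a separate administration period. The home doses are different: Table 2 marks surgical FVIII prophylaxis in the Month 1 column, under the follow-up heading.

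**The comparison with prophylaxis is only for scale.** Section 13.5.4 plans no comparison with prior prophylaxis. That is correct, and the percentages should be read in that way.

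**Conclusion.** The point holds in limited form. Section 13.5.4 uses a single count-based measure although the data for amount and reason are collected, and it includes at least the home FVIII given to cover the procedure. For a patient with no later use, this adds about 4 (once daily) to 8 (twice daily) uses per year at Week 52, or about 3% to 15% of a 52 to 156 uses-per-year prophylaxis frequency. The estimate rests on the Section 9.2.4 frequencies, a Day 7 visit and follow-up starting after Day 3.

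A reader might go further and infer that the measure favours or penalises good responders, or distorts dose decisions. The documents do not support that. The offset is the same absolute amount at any level of later use, Section 13.1 plans no hypothesis testing, and the escalation rules in Section 6.4 use safety and FVIII activity. What suffers is the interpretation of a descriptive secondary endpoint. The change is worth making because it is cheap.

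**What to change.** In Section 13.5.4:

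1. Report annualised total IU and IU/kg alongside the annualised number of infusions.
2. Leave FVIII recorded with the reason of perioperative cover for the SIG-001 procedure out of the annualised figures, and report it separately. Keep treatment of bleeds in the figures whenever it occurs. Leave the follow-up time unchanged, so that it remains the one used for the ABR in Section 13.5.3.

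The cost is wording. Dose, product and reason are already recorded under Section 10.2.2, and weight is collected under the Schedule of Assessments. Section 7.5.1 already provides for cover that runs on: "If FVIII therapy is continued after the Week 1 visit, the reason for continuation will be recorded". No dosing rule changes.

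There are three downsides. The exclusion works only if the reason is recorded clearly for each use in the first weeks, including in hospital. IU/kg may differ between product types, so the infusion count should stay beside it. And the 12-month historical IU rests partly on patient recollection, which limits any before-and-after comparison.
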